**Evaluation protocol**

**Evaluating institution: University of Kent**

**Principal investigator(s): [name]**

**YEF trial protocol for efficacy and effectiveness studies**

Project title	Mixed method, two level, individually randomised controlled trial of a trauma informed intervention, Trauma Recovery Model Relationship Building Together, versus business as usual for adolescents and young adults served by Bridgend Youth Services.
Developer (Institution)	Bridgend County Borough Council
Evaluator (Institution)	University of Kent
Principal investigator(s)	[name]
Protocol author(s)	[name], [name], [name], [name]
Trial design	Two level, two arm individually randomised controlled trial with concurrent qualitative evaluation.
Trial type	Efficacy
Evaluation setting	Youth services including youth justice, edge of care, youth development, early help and children’s services.

Target group	10-18 years (extended to 10-21 years in youth development services).
Number of participants	80 staff and 562 young people.
Primary outcome and data source	Number of delinquent offences in the past 6 months derived from the Self-Report Delinquency Scale (SRDS) at month 6.
Secondary outcome and data source	
Young Person:
 
Number of delinquent offences in the past 12 months derived from the SRDS at months 6 and 12.
 
Self-report behaviour and personality attributes (overall emotional and behavioural difficulties, emotional symptoms, conduct problems, hyperactivity, peer relationships, prosocial behaviour, externalising behaviours, internalising behaviours) derived from the Strengths and Difficulties Questionnaire (SDQ) at month 6 and 12.
 
Self-report non-psychotic mental health derived from the General Health Questionnaire (GHQ12) at months 6 and 12.
 
Self-report wellbeing derived from the Short Warwick Edinburgh Mental Wellbeing Scale (SWEMWBS) at month 6 and 12.
 
Self-report family cohesion, expressiveness and conflict derived from the Brief Family Relationship Scale (BFRS) at month 6 and 12.
 
Self-report Client Service Receipt Inventory (CSRI) to assess police involvement at month 6 and 12 (arrests, cautions, charges, court attendance), educational outcomes (suspensions, exclusions, managed moves) and employment status.
 
Staff
 
Self-report Attitudes Related to Trauma Informed Care

	
(ARTIC) measured before training, and at month 6 and 12 after training.
 
Self-report Short Warwick Edinburgh Mental Wellbeing Scale (SWEMWBS) before training and at month 6 and 12 after training.
 
Staff turnover throughout the trial and staff absence throughout the study period.

--	--

### Protocol version history

Version	Date	Reason for revision
1.1	05/02/24	Inclusion of Children's Services as additional service
1.0 [original]	23/01/24	

## Study rationale and background

Exposure to Adverse Childhood Experiences (ACE) in childhood has been found to have a strong association with a range of health behaviours and outcomes, including: early onset of alcohol use (Dube et al., 2006), binge-drinking (Bellis et al., 2014a, Bellis et al., 2014b, Bellis et al., 2014c), illicit drug use (Dube et al., 2003), depression (Anda et al., 2002, Chapman et al., 2004, Fang et al., 2016, Schilling et al., 2007); low life satisfaction (Bellis et al., 2014c) unintended teenage pregnancy (Bellis et al., 2014a, Bellis et al., 2014b), HIV risk behaviours (Fang et al., 2016), as well as a range of non-communicable diseases (Brown et al., 2010, Dong et al., 2004) and premature death (Brown et al., 2009). There is also evidence of a relationship between ACE and future violent behaviour, both as a victim and perpetrator; in Wales those who have experienced four or more ACE were found to be 15 times more likely to have been the perpetrator of a violent incident (Bellis et al., 2015). A study of almost 12,000 young offenders (Fox et al., 2015) found that, on average, exposure to each additional ACE increased the risk of becoming a serious, violent, or chronic young offender by 35%.

Trauma informed practice aims to address the consequences of adverse childhood experiences by changing the relationship between practitioners and participants and addressing stigma to create a safe environment for young people to express their emotions and understand the relationship between their emotions and behaviour (Skuse and Matthews, 2015). This safe environment allows those who experienced trauma to see adults in a more positive light and aims to disrupt the transition from poor emotional regulation to dysfunctional behaviour.

The Youth Justice System in England and Wales works to prevent offending and re-offending by those under the age of 18 years. The latest available data indicates that there were 19,000 arrests of young people in 2019, which is an 82% drop from 2009 (Youth Justice Board, 2020). Reasons for this decrease include a police focus on more serious offences, usually committed by adults, and a more child-centric approach to policing, including the use of community resolution outcomes and diversion from criminal justice (Sutherland et al., 2017). Of these, boys made up 83% and the average age was 15.3 years. Over the same period there were 11,000 first time entrants, first reprimand or warning of community conviction, to the Youth Justice System which is a reduction of 84% since 2009 (Youth Justice Board, 2020). It is estimated that 38.5% of new offenders go on to re-offend after serving their initial sentence (Youth Justice Board, 2020). The Crime and Disorders Act 1998 is clear that the principle of youth justice is prevention; diverting young people away from youth justice and addressing their core needs through the provision of youth orientated services are a critical part of achieving this goal.

The Trauma Recovery Model (TRM; (Skuse and Matthews, 2015)) and Enhanced Case Management (ECM) are psychology-based, trauma-informed means of working with young

people with complex needs who are suspected of or known to have experienced trauma. Delinquent behaviour and offending are seen as responses to trauma and the model aims to build relationships with young people that are sensitive, empathetic, and non-punitive. The model involves the sequencing of interventions to meet the young person's needs.

Key elements of ECM, using the TRM, include case formulation with, and ongoing supervision by, an experienced psychologist, and sharing the case formulation across multiple agencies working with the young person. The key aim is to ensure that any professional interactions and interventions are designed to align with the young person's developmental and mental health needs. Creating positive experiences and strong trusting relationships between young people and professionals are key components in ensuring young people are capable and willing to engage in supportive intervention and to take advantage of prosocial opportunities to not only reduce delinquent behaviour but also improve across a spectrum of psychosocial domains. Several Youth Offending Teams (YOT) across England and Wales have started to implement TRM and ECM and all YOTs in Wales have had some training in the approach.

Previous research in youth justice services has found high levels of staff fidelity and stakeholder acceptability of the ECM approach, and changes in practitioner perspectives from viewing offending behaviour as being fixed and intentional to viewing it as adaptive and changeable (Cordis Bright., 2017). Improvements for young people across a variety of domains were also found: improved relationships with practitioners and families, greater confidence in accessing support, improved emotional regulation and greater positivity about the future (Cordis Bright., 2017, Glendinning et al., 2021). Yet these previous studies have used research designs that lack the scientific rigour to assign causality to the intervention. Previous research has tended to be simple before and after studies with no control comparator; hence, despite strong theoretical underpinnings the approach does not have strong evidence of effect. Further, previous evaluations have tended to focus on ECM alone in YOTs rather than the combination of TRM and ECM across multiple services meeting the needs of a broad range of young people.

What is needed is scientifically rigorous research that provides clear evidence of whether TRM and ECM works in adolescent and young adult populations, using a tiered approach across multiple services with TRM alone for the least complex cases and ECM for the most complex cases as in the Relationship Building Together (RBT) model. The proposed research aims to address these key questions. We propose a mixed method, two-level, individually randomised controlled trial of a trauma informed intervention, Relationship Building Together, versus business as usual (BAU) for adolescents and young adults served by Bridgend Youth Services.

## **Intervention**

The intervention, RBT, involves a model of practice that aims to avoid stigmatising and criminalisation of young people through the identification and formulation of a sequence of

interventions that respond to the childhood trauma experienced by the young people. Greater detail on the theoretical framework and the intervention approach is available here: <https://www.trmacademy.com/#theModel> and the hypothesised theory of change is articulated in figure 1. The intervention builds on work already delivered in youth justice services in Bridgend over the past 18 months, to include a population of young people in other services: Edge of Care, Children's Services, Youth Development, and Early Help – who may be starting to display challenging behaviour as a response to their trauma.

Practitioners are randomly allocated to receive training or not using a secure on-line randomisation service employing a minimisation algorithm which means staff are allocated to ensure balance between service and specialisation. 50% are allocated to RBT training and 50% continuing with BAU. The initial training is delivered to 35-40 staff members over 3-days by specialist trainers from the Trauma Recovery Model Academy. Trainers are experienced practitioners; social workers, clinical psychologists and youth workers who have developed and delivered the RBT intervention for many years across several different services working with young people. Training aids practitioners to understand the impact of prior trauma on the young person's behaviour, the development of strategies to reduce the behavioural consequences of trauma, building relationships and communication, the principles of case management and how to employ evidence-based interventions to promote positive development, and ensuring trauma histories are embedded in the case management process.

Up to ten senior members of staff, consisting of managers for each service and those currently responsible for core assessment of need on referral, will receive an additional two-day training with the aim of becoming trauma leads and champions within their departments. These staff will receive monthly mentoring throughout the project and shadowing from other similar services in Wales. These trauma leads will take responsibility for the core assessment of need, case formulation meetings and embedding trauma informed practice within services.

Practitioners engage in trauma screening for any young person allocated to the intervention arm, and dependent on the young person's need the intensity of intervention is agreed. Tier 1, the lowest tier of need, includes young people who have evidence of past trauma, but it is not complex (it may be due to temporary family or financial difficulties for example), and they have experienced periods of recovery. Tier 2 involves young people who have more complex trauma with little evidence of periods of recovery, often a result of family breakdown or significant traumatic events; these young people require more intensive intervention involving an in-house multi-disciplinary team. Young people in tier 3 are the most complex, they will have a significant history of trauma, often as a result of neglect, breakdown, or involvement in criminal activity, with no evidence of any periods of recovery, and intervention needs to be both multi-disciplinary and led by a clinical psychologist. A brief comparison of BAU and different tiers of intervention is provided in table 2 and more detail provided below.

Tier 1 involves guidance and support from the trauma leads to the case manager and other relevant professionals involved in the case, on engaging with and supporting the young person in a trauma-informed manner. The trauma leads assist to ensure that assessments and reports are conducted with a trauma-informed perspective. This involves considering the young person's trauma history, understanding the potential triggers, and incorporating trauma-related information into the assessment process. This approach helps to gain a comprehensive understanding of the young person's needs and informs the development of an effective intervention plan. Trauma leads will review the progress of interventions mid-intervention against the Trauma Recovery Model (TRM) framework. This assessment helps identify any necessary adjustments or modifications in the intervention plan, ensuring that it remains responsive to the young person's evolving needs and progress.

In addition to trauma screening, tier 2 involves a relationship-based mapping exercise led by the trauma lead that plays a crucial role in understanding the young person's life experiences, trauma history, and developmental needs. The trauma lead organises a multi-agency meeting with professionals from various disciplines involved in the young person's care. This may include social workers, educators, medical professionals, and other relevant professionals who have been in the young person's or family's life. The meeting serves as a platform for collaborative information sharing and decision-making.

During the meeting, the attendees collectively create a timeline that captures significant events in the young person's life, starting from pre-birth. This timeline includes not only the young person's experiences but also the mother's experiences prior to giving birth. The timeline helps identify potential sources of trauma, understand their impact, and establish patterns or triggers that may affect the young person's well-being. Professionals will also be asked to provide input on the young person's emotional, social, and cognitive age based on their observations and professional expertise. This information helps develop a comprehensive understanding of the young person's overall development and potential developmental gaps resulting from trauma.

To visualise and timeline trauma events, an interactive system is utilised. The system allows attendees to collaboratively add trauma events, notes, and observations onto a shared digital platform. This visual representation enhances the understanding of the young person's experiences and facilitates effective communication among the professionals involved. Developmental mapping is also conducted to assess the young person's current developmental stage and to identify any areas where trauma has impacted their development. This mapping process helps identify strengths, vulnerabilities, and areas requiring targeted interventions. Importantly, the developmental mapping can be updated and followed throughout the young person's journey into adulthood, providing a comprehensive framework for long-term support.

Based on the information gathered from the relationship-based mapping exercise, trauma leads generate a formulation report. This report provides an in-depth profile of the young person, including their trauma history, developmental strengths and challenges, and recommendations for intervention. The report highlights trauma-informed strategies and interventions that are tailored to the young person's specific needs and are developmentally appropriate. The recommendations outlined in the formulation report are implemented by all professionals involved in the young person's care. This ensures a consistent and coordinated approach to trauma recovery and intervention. Professionals collaborate closely, sharing information and working together to provide continuous support and appropriate interventions throughout the young person's journey.

All services involved commit to maintaining a continuity of trauma intervention. This means that the young person receives consistent support from various professionals over a universal designated period. Regular reviews are undertaken at specific intervals to assess the effectiveness of interventions, adjusted if necessary, and ensure that the young person's evolving needs are addressed appropriately.

Tier 3 is similar to Tier 2, but with the addition of a trauma specialist clinical psychologist who leads the mapping exercise. The psychologist will produce the formulation report based on the information discussed in the timelining exercise, providing further insights and recommendations for intervention.

Business as usual is usual practice, it involves no trauma screening or developmental assessment and focusses on the assessment and mitigation of risk. It differs across services, but it focusses on the young person and family, based on the referral with no multi-agency involvement in case formulation. Interventions can be relatively short term, for Edge of Care services, where crisis interventions might last 6-8 weeks or they can be longer term, 6-9 months, for Youth Offending Services. Interventions differ across services. In Early Help the approach is focussed on early intervention, providing practical advice and support for young people and their families, and acting as a liaison between different services. Youth Development Services are often delivered within youth centres and involve signposting and mentoring, addressing issues such as health and wellbeing, education, employment, and housing. Edge of Care Services and Children's Services are social work focussed aiming to avoid a young person going into care or managing child protection or child in need procedures, interventions encompass a range of approaches including family and young people's support, Signs of Safety, placement support, social work assistant interventions, family therapy and the involvement of young people's mental health services. Youth Justice Services deliver interventions for young people involved with the criminal justice service, with the aim of preventing re-offending. Multi-disciplinary interventions focus on wellbeing and resilience, restorative justice, and prosocial engagement.

Figure 1: RBT Theory of Change

[figure not shown]

Table 2: RBT Tiers of intervention compared to BAU.

Business as usual	TRM Tier 1 Trauma Aware (TA)	TRM Tier 2 Relationship Building Practice (RBP)	TRM Tier 3 Enhanced Case Management (ECM)

 
 Assessment and Intervention without developmental mapping.
 
 Responding to risks and focus on how to manage risk.
 
 Different plans for different services.
 
 Child / family supported by practitioner with the usual training they have been offered.
 
 Formulates a plan of work based on the referral. No multi-agency meeting or developmental mapping.
 
 Undertakes direct work with the child.
 
	
 
 Trauma Recover Model (TRM) Training.
 
 Access to clinical psychology support – group supervision.
 
 Consistent plans and tool kit for practitioners across the services.
 
 Input, advice, and guidance available from trauma lead.
 
	
 
 Trauma Recover Model Training.
 
 Multi-agency case formulation meeting chaired by trauma lead.
 
 Developmental mapping and TRM assessment informing the planning to undertake direct work.
 
 Ongoing consultation/supervision with the trauma lead.
 
 Summary report of case formulation meeting.
 
 Ongoing multi-agency review meetings.
 
 Access to clinical psychology support.
 
	
 
 Trauma Recover Model Training.
 
 Clinical Psychologist led.
 
 Multi-agency case formulation meeting.
 
 Ongoing consultation and supervision with the clinical psychologist.
 
 Developmental mapping and TRM assessment informing the planning.
 
 Full clinical psychologist report.
 
 Ongoing multi-agency review meetings.
 

## Impact evaluation

### Study objectives

1. To conduct a prospective RCT to evaluate the efficacy of the Relationship Building Together (RBT) approach compared with business as usual (BAU) on offending behaviour, measured using the Self Report Delinquency Scale (SRDS), over 6- and 12-months post-randomisation, in a population of young people, aged 10-21 years inclusive, accessing services provided by Bridgend Youth Offending Team, Bridgend Youth Development Services, Bridgend Early Help Hubs, Bridgend Edge of Care Services, and Bridgend Children's Services.
2. To evaluate the efficacy of the RBT versus BAU in terms of emotional regulation, peer, prosocial, conduct, hyperactivity, internalising and externalising behaviours (SDQ), wellbeing (SWEMWBS), psychological health (GHQ12), family cohesion (BFRS), school, work, and criminal justice involvement (CSRI), in a population of young people, aged 10-21 years inclusive, accessing services provided by Bridgend Youth Offending Team, Bridgend Youth Development Services, Bridgend Early Help Hubs, Bridgend Edge of Care Services, and Bridgend Children's Services, at 6- and 12-months post randomisation.
3. To evaluate the impact of RBT versus BAU on staff perception of trauma informed care (ARTIC), staff wellbeing (SWEMWBS), staff turnover and staff absence in the 6 and 12 months after training across Bridgend Youth Offending Team, Bridgend Youth Development Services, Bridgend Early Help Hubs, Bridgend Edge of Care Services, and Bridgend Children's Services.
4. To conduct a micro-costing exercise to provide estimates of the cost of delivering the intervention from the perspective of the intervention delivery organisation.
5. To develop a prognostic model exploring the baseline demographics (age, sex, ethnicity, IMD), psychological (SDQ, GHQ12, ACES), therapeutic alliance (TASC-r) and family factors (BFRS) that may impact observed outcomes and using the results to elaborate mechanisms of change and where appropriate revise the intervention logic model.
6. To conduct a latent class analysis to explore potential interactions between population subgroups, intervention received, and outcomes observed.

7. To assess and report on any iatrogenic or adverse effects of the control and intervention. Adverse events include but are not limited to; concerns for the physical and emotional wellbeing of a child, self-harm, suicidal ideation, or death, physical, mental, and emotional abuse as a victim or perpetrator, actual or intended violent offences as a victim or perpetrator. Ensuring that any serious events are brought to the attention of the funder in accordance with their safeguarding policy <https://youthendowmentfund.org.uk/wp-content/uploads/2023/04/2304-YEF-Safeguarding-Policy.pdf>.

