The assessment battery takes 15 minutes to complete on average based on the use of a similar question battery with an adolescent population in other studies. Each young person will be supported during completion, at baseline by staff in the services and at 6- and 12-month by researchers who will be blind to participant allocation. Research staff will provide training in baseline data collection to staff in Bridgend across the five services through an interactive in-person training session and this will include a training manual and on-going support. At the end of each assessment point and at the end of any qualitative interview the young person will be provided with an opportunity to debrief and reflect on the impact of answering the questions. This debrief is designed to identify any negative impacts of reflecting on themselves and any potential re-traumatisation. If issues are identified, the potential adverse event standard operating procedure will be activated, and trauma leads in each service asked to conduct an assessment and provide any necessary intervention. All adverse events in both arms of the study will be recorded and reported.

In addition to key demographics (age, sex, ethnicity, and IMD) that will be assessed at baseline we will assess the exposure to adverse child experiences assessed on entry to the service using existing records.

Six months after randomisation, in both arms of the study, young people will be contacted by phone or email by researchers and asked to complete the short revised therapeutic alliance scale for children (TASC-r; (Shirk and Saiz, 1992)), this assesses the quality of the relationship between the young person and staff member. Therapeutic alliance is a strong predictor of outcome, and this will be used in the prognostic model (objective 5).

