### **Ethics and registration**

The study will be conducted in accordance with the principles of Good Clinical Practice, the Declaration of Helsinki and Caldicott principles. Participants will only be recruited to the study once independent full ethical approval has been granted by the University of Kent Social Research Ethics Committee and the trial will be registered in a recognised trial registry. Trial methods and data collection instruments will be assessed by our Youth Advisory Board and their recommendations for changes will be incorporated.

We will ensure participants do not feel coerced to participate in the study. Once a participant is referred to the service any consent or assent to participate in the trial is theirs solely to make. Not consenting to the research will not impact on the BAU they receive, and this will be explained verbally and in writing. If a participant does consent it will be made clear that they can withdraw consent at any time during data collection for the study. Participants will

be able to withdraw from any interventions and still provide follow-up data; withdraw, and have data already completed included in the trial analysis but provide no further additional data; or withdraw completely and have data already collected removed from the analysis.

We will minimise the potential for participants and staff to experience any adverse or iatrogenic events. In our experience of conducting similar studies in similar populations the risk of adverse events is low, as is the risk of iatrogenic events. We will implement a standard operating procedure for the reporting of adverse events that involves an independent experienced third-party making recommendations on the severity of any event and whether they are associated with the trial. All staff involved in the study will have enhanced DBS accreditation and will be familiarised with safeguarding practice and procedures. Each service will have a named trauma lead in each site available for assessment and intervention if re-traumatisation is suspected.

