To explore the proposed mechanism of change we will conduct a prognostic linear regression analysis to model the relationship between pre-randomisation factors; age, gender, ethnicity, IMD, SRDS, SDQ, BFRS, GHQ and observed outcomes at 6- and 12- months respectively on the primary outcome at either 6- or 12-months. Interaction terms with allocation arm will be included in the analysis, and a significance level of 0.1 will be used to determine which factors are to be included in the regression model. This analysis will be augmented by an additional

analysis including participants in the RBT arm only using the same pre-randomisation factors but also including process measures of compliance, therapeutic alliance, and interventionist attitude to trauma informed practice.

Interim analyses and stopping rules

No interim analyses are planned. The trial will only be stopped if evidence emerges of a serious adverse event associated with participation in the trial. As the intervention has already been implemented in practice with youth offending populations there is no evidence at the outset that a serious adverse event is likely to occur.

Longitudinal follow-up analyses

Assessments are conducted at baseline, prior to randomisation and then again at months 6 and 12, with 6-months being considered the primary endpoint. Table 2 provides an overview of what measures are being conducted at each time-point.

Outcome	No of items	Baseline	Six months	Twelve months
Primary				
Self-reported delinquency (SRDS) ¹	36	✓	✓	✓
Secondary				
Strength and Difficulties (SDQ) ¹	25	✓	✓	✓
Wellbeing (SWEBWMS)	7	✓	✓	✓
Psychological Distress (GHQ12)	12	✓	✓	✓
Family environment (BFRQ)	16	✓	✓	✓
Receipt Inventory (CSRI)	8	✓	✓	✓
Staff attitudes to trauma informed care (ARTIC)	35	✓	✓	✓
Staff wellbeing (SWEBWMS)	7	✓	✓	✓
Staff turnover & absence	2	✓	✓	✓
Exploratory				
Adverse childhood experiences (ACE-Q)	10	✓		
Process				
Therapeutic relationship	12		✓	
Proportion of sessions planned & delivered	1		✓	✓

Imbalance at baseline

Rather than just assume the randomisation has worked, we will assess observed balance by comparing the means and distributions of the groups created by randomisation for both participants and staff. If they are systematically different across those variables we observe – e.g. always larger / smaller in one group - then that would suggest the randomisation has not been successfully implemented. Baseline equivalence following randomisation will be

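### Adverse events have no onset rule and overlap with referral reasons and offending; with screening and review only in RBT, counts by arm are at risk of detection bias

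*Protocol*

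**What the plan says.** Protocol, Study objectives, objective 7, is "To assess and report on any iatrogenic or adverse effects of the control and intervention". Its list of events is expressly not exhaustive. It includes "concerns for the physical and emotional wellbeing of a child, self-harm, suicidal ideation, or death", abuse as victim or perpetrator, and "actual or intended violent offences as a victim or perpetrator".

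Protocol, Intervention, describes Edge of Care and Children's Services as "aiming to avoid a young person going into care or managing child protection or child in need procedures". The same section says "Practitioners engage in trauma screening for any young person allocated to the intervention arm". In tiers 2 and 3 it adds a life timeline reaching back before birth, a multi-agency meeting and continuing multi-agency reviews. BAU has none of these and centres on assessing and mitigating risk. Protocol, Participants, places the screening after randomisation, and Protocol, Randomisation, says that staff cannot be blinded.

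Protocol, Secondary outcomes, provides a debrief at the end of each assessment and states "All adverse events in both arms of the study will be recorded and reported". Protocol, Ethics and registration, gives an independent third party the task of advising on severity and on relation to the trial, and says that in similar studies "the risk of adverse events is low, as is the risk of iatrogenic events".

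The SAP mentions adverse events only under Interim analyses and stopping rules: "The trial will only be stopped if evidence emerges of a serious adverse event associated with participation in the trial". It specifies no table or analysis of them.

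**The concern.** Two separate features combine.

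First, the definition does not distinguish an event from the participant's starting point or from the trial's outcome. A welfare concern or history of abuse may be the reason a young person was referred. A violent offence may be both an SRDS item and an adverse event. Neither document says that an event must begin or worsen after randomisation.

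Second, the arms are not observed in the same way. The RBT-only steps are meant to bring trauma, neglect and family breakdown to light, and the continuing reviews give further occasions on which a current problem can surface. Without an onset rule, old history disclosed during mapping can be logged as an event in RBT with no equivalent route in BAU.

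At stake is what can be said about harm. If RBT shows more recorded events, a reader cannot tell harm from better detection. If the counts are equal, better detection in RBT could be hiding a real reduction.

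**Working it through.** There is no adverse-event rate, sample size or power figure in either document, so there is nothing of the plan's own to reproduce. The check has two parts.

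**Part 1: the overlap and the routes of detection, set side by side.**

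- Definition against population: general welfare concerns and abuse are events under objective 7, and two of the five services manage child protection or child in need cases.
- Definition against outcome: violent offending as a perpetrator is an event, and the primary outcome is the quantity of offences on the SRDS at 6 months.
- Onset: no rule in either document.
- Routes common to both arms: the debrief at each assessment (at months 6 and 12 by blinded researchers), and the commitment to record events in both arms. BAU risk assessment can also surface current concerns.
- Routes in RBT only: trauma screening for all; timeline, mapping and multi-agency reviews in tiers 2 and 3.
- Reach of the common route: the debrief is described as picking up distress or re-traumatisation caused by answering the questions. It is not described as asking about abuse, self-harm or violence since the last contact.

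The overlap alone should fall equally on both randomised arms, so it adds noise. Bias needs unequal detection, and the RBT-only routes make that possible.

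**Part 2: how large the effect could be.** Let the true risk p be the same in both arms, with shares s_R and s_B of events coming to light.

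Recorded risk = p × s, so recorded risk ratio = (p × s_R) / (p × s_B) = s_R / s_B.

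Per arm: 562 / 2 = 281 (Protocol, Sample size calculations, with 1:1 allocation). All detection shares and p = 20% are assumptions.

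| Detection RBT / BAU | Ratio | Recorded events at p = 20% |
|---|---|---|
| 70% / 60% | 0.70/0.60 = 1.17 | 0.14 × 281 = 39 v 0.12 × 281 = 34 |
| 80% / 60% | 0.80/0.60 = 1.33 | 45 v 34 |
| 70% / 50% | 0.70/0.50 = 1.40 | 39 v 28 |
| 80% / 50% | 0.80/0.50 = 1.60 | 0.16 × 281 = 45 v 0.10 × 281 = 28 |
| 80% / 80% | 1.00 | 45 v 45 |
| 70% / 90% | 0.70/0.90 = 0.78 | 39 v 0.18 × 281 = 51 |

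The SAP plans no test of these counts. If someone ran a two-sided 5% comparison of proportions at 281 per arm, detection of 90% against 70% (ratio 1.29) would give a nominally significant false excess in RBT with probability of about 9%, 14%, 25% and 38% at true risks of 5%, 10%, 20% and 30%. With equal detection the figure is 2.5%.

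This model covers only events missed in one arm. History logged as a new event in RBT would add to it, but the documents give no rate for that.

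**The case against.** The other side has substantial points.

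- **No arm comparison is promised.** Objectives 1 to 3 are worded as comparisons; objective 7 is to assess and report. This stands as a matter of wording. But effects of the control and the intervention can hardly be reported without counts by arm, and readers will compare them.
- **A reader might infer that only RBT is screened for adverse events.** The documents do not say so. The RBT-only screen concerns trauma history and sets the tier; the debrief and recording cover both arms, and BAU assesses risk. This stands, although without an onset rule disclosed history can still be logged, and continuing reviews can surface new events.
- **The overlap is balanced by randomisation**, which is stratified by service, and the primary analysis uses the SRDS alone. This stands: double counting does not touch the primary result.
- **An independent third party judges relatedness**, and stopping requires an event associated with participation. This protects the stopping decision against referral concerns present at entry. It does not settle onset, source or overlap with the outcome, and that party's blinding is not stated.
- **The statement that risk is low might be read as contradicting the definition.** It reports experience from similar studies, so it is an expectation and there is no contradiction.
- **The operating procedure is not included** and may already hold some of these rules. This stands as a caveat.

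**Conclusion.** The concern holds as a risk of detection bias in event counts by arm, together with a definition that has no onset rule and no separation from referral reasons or the primary outcome. More recorded events in RBT is the most plausible direction, because the additional post-randomisation routes are all in that arm and staff are unblinded.

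It is tempting to conclude that the comparison is biased against RBT, or that the adverse-event data are unusable. The documents do not support either. They give no detection shares, BAU has its own risk assessment, and the ratio is 1.17 to 1.6 only if detection is assumed to be 70-80% against 50-60%. It is 1.0 with equal detection and 0.78 if 70% against 90% is assumed. There is also no basis for saying that the two sources of events will be pooled; the plan is silent on how they will be tabulated.

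The change is worth making because it costs little and because source and onset are hard to reconstruct later.

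**What to change.** Leave safeguarding reporting and the stopping text as they are. Then:

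1. Add two fields to the event form: source of detection, and onset before or after randomisation.
2. In the SAP, report events by arm, counting only those with onset or worsening after randomisation.
3. Tabulate them separately by source: research contact common to both arms; RBT-specific screening, mapping or review; other service contact or records. Report deaths and serious events in full, whatever the source.
4. Report SRDS offences as the outcome and do not count them again as adverse events.
5. State that unequal detection limits the interpretation of any difference between arms.

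Do not rest the comparison on the existing month-6 and month-12 debrief alone. It is aimed at distress from answering the questions, and it would miss deaths and participants lost to follow-up.

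If the operating procedure already contains any of these rules, the SAP need only cite them. The cost is two form fields, some SAP wording, and fewer events in the table used to compare arms.
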